4.1.2 Composite adverse events until day 30 ("CAE30", first secondary endpoint)

will be encoded as the patient level Boolean inclusive disjunction ("OR") of the following eight binary (true/false) single adverse event endpoints (1a) all-cause in-hospital mortality, (1b) all-cause mortality after discharge (as available), (2) septic shock (vasopressor use for > 1 h), (3) mechanical ventilation (via endotracheal tube for respiratory failure), (4) needed dialysis, (5) lung abscess/empyema/cavitation/necrotizing pneumonia or (6) hospital readmission.

In the case a patient is enrolled with mechanical ventilation, such an event is not considered to be an adverse event due to its occurrence before any intervention. If the patient is then extubated during their hospital stay, re-intubation is only classified as an adverse event if it occurs at least 24 hours post extubation.

In the case a patient is enrolled with septic shock, such an event is not considered to be an adverse event due to its occurrence before any intervention. If the patient then has a resolved septic shock during hospital stay, developing a new septic shock is only classified as an adverse event if it occurs at least 24 hours post resolution of the initial septic shock.

In the case a patient develops a safety adverse event at any point on the day of enrollment post randomization, such an event will be classified as an adverse event.¹

The variable CAE30 mirrors the safety endpoint for pneumonia used in the study ProACT [Huang2018]. And, also as in ProACT, the endpoint will be analyzed in the form of study-arm-specific proportions, see Section 4.3ff.

4.1.3 Antibiotic exposure at discharge (“prescribedABx”, second secondary endpoint) will be encoded as the proportion of patients per study arm (PCT arm, control arm) with antibiotic prescription for pneumonia treatment at discharge from index hospitalization.

The numerical endpoint **antibiotic duration** is the third secondary endpoint, see definition in Section 4.1.1.

4.1.4 The fourth secondary endpoint “antibiotic duration”
will be computed per patient as described in Subsection 4.1.2.

4.1.5 The fifth secondary endpoint “days of therapy per 1000 patient days”
will be computed per patient i as follows (i: index distinguishing different study patients):

$$\text{DoT}(\text{ patient i }) = \text{antibiotic duration}(\text{ patient i }) / \text{los30}(\text{ patient i }) \times 1000$$

with length of stay of patient i

$$\text{los30}(\text{ patient i }) = \min(30, \text{number of hospital days of patient i}).$$

Note that DoT(patient i) is not capped by 1000 because antibiotic duration also includes antibiotics days prescribed at discharge while los30 only counts the number of in-hospital days.

4.1.6 The sixth secondary endpoint “antibiotic days prescribed at discharge”
will be computed per patient as the number of prescribed days of antibiotic treatment at hospital discharge counting all days with antibiotics marked “to treat pneumonia”.

4.1.7 The seventh secondary endpoint “treatment or readmission for CDI until day 30 after discharge”

will be encoded in binary Boolean form (“true”: patient treated or re-hospitalized for CDI until day 30 after discharge, otherwise “false”).

4.1.8 The eighth secondary endpoint “length of stay in hospital until day 30” (“los30”)

¹ It is unlikely that early safety adverse events on the day of patient randomization can be prevented or induced by the specified PCT algorithm. Accordingly, to control for the impact of such early adverse events on study safety results, we will perform an additional safety analysis focused on safety adverse events that occur at least 24 hours after patient randomization (CAE30’), see Section 4.6.

will be computed per patient as described in the previous subsection.

4.1.9 The ninth secondary endpoint “length of stay in ICU” (“losICU30”)

will be computed analogously to los30 but will only count days on ICU:

$$\text{losICU30} = \min(30, \text{number of ICU days of patient } i).$$

4.1.10 The tenth secondary endpoint “ICU admission until day 30”

will be encoded per patient in binary form (“true”: patient admitted to ICU within study follow-up time of 30 days, otherwise “false”).

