Primary Objective	Determine the difference in antibiotic exposure and healthcare cost and assess safety by comparing antibiotic prescription guided by a (i) PCT algorithm + stewardship team (intervention) or (ii) standard guidelines (control) in hospitalized patients with suspected or confirmed LRTI.
Study Design	Prospective, multi-center, randomized-controlled interventional trial
Enrolling Wards	ED, admitted floor and ICU teams
Intervention	Addition of previously validated PCT algorithms to clinical assessment to guide the discontinuation of antibiotics in patients with suspected or confirmed pneumonia.
Primary Endpoint	Proportion of patients with short treatment of pneumonia with antibiotics (less than 4 days, "shortABx")
Secondary Endpoints	
 1. Composite safety adverse event rate at 30 days (CAE30). The composite endpoint includes: 
 a. All-cause in-hospital mortality b. All-cause mortality after discharge (as available) c. Hospital readmission d. Septic shock (vasopressor use for > 1 h) e. Mechanical ventilation (via endotracheal tube for respiratory failure) f. Required dialysis g. Lung abscess/empyema 2. Antibiotic exposure at discharge 3. Antibiotic duration 4. Days of Therapy per 1000 patient days (inclusive of antibiotics prescribed at discharge) 5. Antibiotic days prescribed at discharge 6. Treatment or readmission for CDI until day 30 after enrollment 7. LOS in hospital until Day 30 8. LOS on ICU until Day 30 9. ICU admission until Day 30
Exploratory Endpoints	All the single variables of the safety endpoint CAE30, see 3.2. "Composite adverse events until day 30"
Healthcare Economic Endpoints	
Costs associated with primary hospitalization, readmission for CDI, and loss of function
 
 • Cost of Antibiotics (total cost of antibiotics per patient inclusive of antibiotic, tubing, IV bag, discharge antibiotic prescription) • Cost of Procalcitonin • Total per patient cost (including blood cultures and mechanical ventilation days)

	
 • Antibiotic ADRs (e.g. CDI) • AB days difference plus prescriptions avoided infection adverse event incidence modeling²⁹ • Cost of readmissions

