4.2.5 Definition 'until day 30'

Day 30 is defined as the thirtieth calendar day after ED or hospital admission.

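### The ICU-stay formula does not deliver ICU days until day 30, and the ICU-admission endpoint has no rule for patients already in ICU at randomisation

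*SAP*

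**What the plan says.** Two secondary endpoints concern the ICU. In SAP 4.1.10 and Protocol 8.2.10, ICU admission is true for a "patient admitted to ICU within study follow-up time of 30 days". In SAP 4.1.9 and Protocol 8.2.9, losICU30 "will be computed analogously to los30 but will only count days on ICU". Its formula is the minimum of 30 and the "number of ICU days of patient", copied from los30, which takes the minimum of 30 and the "number of hospital days of patient i". The protocol synopsis and Protocol 3.3 call the endpoint "LOS on ICU until Day 30".

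Four other passages bear on how these are read:

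- Protocol 4.2.5: "Day 30 is defined as the thirtieth calendar day after ED or hospital admission".
- Protocol 4.1: screening takes place one day after admission to an inpatient bed, so randomisation comes later than the event from which day 30 is counted.
- Protocol synopsis, enrolling wards: "ED, admitted floor and ICU teams". The indication also names the ICU.
- SAP 4.1.2: for a patient enrolled on ventilation or in septic shock, "such an event is not considered to be an adverse event due to its occurrence before any intervention". Neither ICU endpoint has a matching rule.

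SAP 4.8 analyses binary secondary endpoints with 2 x 2 tables, a chi-square or Fisher test, and proportions with intervals. It does not adjust for ICU status at baseline.

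**The concern.** The intervention guides the stopping of antibiotics, so readers will look at ICU use for signs of harm. CAE30 does not include ICU admission. A patient who deteriorates and moves to the ICU without intubation, shock, dialysis or another CAE30 event is seen only in the ICU endpoints.

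The two definitions fall short in different ways. The losICU30 formula contradicts its own label, because a cap of 30 on a total is not a cut-off at day 30. The admission endpoint leaves one group unclassified: patients who entered the ICU before randomisation. If they count as events, they add the same expected proportion to both arms, and the endpoint becomes less able to show a change in new ICU admissions. The plan recognises this problem for ventilation and shock but not for ICU status.

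**Working it through.** The documents give no rate, power or sample size for either ICU endpoint, so there is no stated figure to reproduce.

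**1. losICU30: label against formula.** Days are counted from admission as day 0. Randomisation on day 2 is assumed.

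| ICU days | Total | Formula min(30, total) | Days through day 30 | Days from randomisation through day 30 |
|---|---|---|---|---|
| 28 to 42 | 15 | 15 | 3 | 3 |
| 20 to 45 | 26 | 26 | 11 | 11 |
| 10 to 44 | 35 | 30 | 21 | 21 |
| 0 to 3 | 4 | 4 | 4 | 2 |
| 0 to 45 | 46 | 30 | 31 | 29 |

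The formula goes wrong for stays that begin late and run past day 30. For a stay that runs unbroken from admission, it nearly agrees with a cut at day 30 (last row). Days before randomisation are included in every case.

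**2. ICU admission: effect of counting patients already in ICU.** Let b be the share already in ICU at randomisation and p the rate of new ICU admission among the others. If patients already in ICU score true:

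- observed rate = b + (1 − b)p
- risk difference = (1 − b)(p_PCT − p_ctrl)

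Scoring them all false gives the same risk difference, because b cancels.

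Inputs: 350 per arm (protocol, maximum sample size) and a two-sided 5% test. Assumed: p = 12% in the PCT arm and 6% in control, b = 10%. The documents give neither p nor b. The pilot data cannot supply b, because they cover only patients not transferred to ICU within 24 hours.

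- Rates: 0.10 + 0.90 × 0.12 = 0.208, and 0.10 + 0.90 × 0.06 = 0.154.
- Difference 0.054; ratio 0.208/0.154 = 1.35.
- Standard error = √(0.208 × 0.792/350 + 0.154 × 0.846/350) = 0.0290.
- Power = Φ(0.054/0.0290 − 1.96) ≈ 46%.

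New admissions only, among the 350 × 0.90 = 315 per arm not in ICU:

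- Difference 0.06; ratio 2.0.
- Standard error = √(0.12 × 0.88/315 + 0.06 × 0.94/315) = 0.0227.
- Power = Φ(0.06/0.0227 − 1.96) ≈ 75%.

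**3. Range over the assumptions.** Each pair compares counting patients already in ICU as events with counting new admissions only, among patients not in ICU.

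| New admission, PCT v control | b | Ratio | Power |
|---|---|---|---|
| 12% v 6% | 10% | 1.35 v 2.00 | 46% v 75% |
| 12% v 6% | 20% | 1.19 v 2.00 | 30% v 70% |
| 12% v 6% | 30% | 1.12 v 2.00 | 21% v 65% |
| 10% v 5% | 5% | 1.49 v 2.00 | 49% v 69% |
| 10% v 5% | 10% | 1.31 v 2.00 | 36% v 66% |
| 15% v 10% | 20% | 1.14 v 1.50 | 21% v 43% |

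At b = 0 the two definitions coincide. The loss grows with b.

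**The case against.** **The plan does not say that earlier ICU admissions count.** A reader might infer that it does. However, the follow-up time in SAP 4.1.10 is not given a start, and elsewhere the SAP ties follow-up to enrolled patients: 2.3.3 allows five follow-up days for the last enrolled patient, and 2.5 speaks of enrolled patients completing 30 days. Protocol 4.2.5 fixes which day is day 30, not when counting begins. This stands. Counting from admission is the likelier reading, since a 30-day period ending on that day begins at admission, but it is not an explicit rule. Under the other reading, a patient already in ICU is still unclassified.

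**The arm comparison is not biased.** A reader might infer that harm is hidden by bias. Randomisation balances baseline ICU status, the ITT risk difference is the same under either coding, and no ratio is planned. This also stands. What remains is lost power, and a ratio nearer 1 if anyone computes one from the reported proportions.

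**Days after day 30 may never be recorded.** The last column of the study plan is day 30, and SAP 2.6 speaks of 30-day follow-up data. This stands too: the formula admits later days, but the documents do not show that they will be collected. Protocol 7.1 lists the number of ICU days without a window.

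**The stakes are limited.** CAE30 already captures death, shock, intubation, dialysis and readmission. ICU time before randomisation should usually be short and adds noise rather than bias. With 15% v 10% and b = 20%, even the repaired endpoint has only 43% power.

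**Conclusion.** The point holds as a defect of definition in two lower-order secondary endpoints. The mismatch between the losICU30 formula and its label is on the page and needs no assumption; in the day 28 to 42 example it is 15 days against 3. The missing rule for patients already in ICU is also on the page. That these patients would score true rests on counting follow-up from admission.

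The size of the power loss rests wholly on assumed rates. Over the scenarios shown, with 5% to 30% already in ICU, power is 21% to 49% when these patients count as events and 43% to 75% for new admissions only. The documents do not support a claim of bias, nor a claim that harm will be missed. Both endpoints lie outside the three-step hierarchy in SAP 2.4, so the primary result, CAE30 and type-I error control are untouched.

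**What to change.** Amend SAP 4.1.9 and 4.1.10 and Protocol 8.2.9 and 8.2.10 together:

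1. Define ICU admission as a first ICU admission after randomisation and by day 30, analysed in patients not in ICU at randomisation.
2. Report ICU status at randomisation by arm, and report ICU readmissions of patients already in ICU separately.
3. Define losICU30 as ICU calendar days from randomisation through day 30.
4. State how deaths before day 30 and ICU days during a readmission are counted.

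The cost is wording and derivation. Protocol 7.1 already collects enrolment and ICU admission dates and times. It lists a count of ICU days but no explicit ICU discharge date, so the sponsor should confirm that each ICU stay can be dated at both ends.

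The downside is that the new-admission analysis omits patients already in ICU, who are likely to be among the sickest enrolled. Because ICU status at randomisation is a baseline characteristic, the randomised comparison among the remaining patients is preserved, and item 2 keeps the omitted group visible.

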4.1.11 Exploratory Endpoints

All the individual variables constituting the composite safety endpoint “composite adverse events until day 30” will be considered as exploratory endpoints and be encoded in Boolean-binary form (true/false).

4.2 Descriptive Statistics

The first step of statistical data analysis will comprise the application of conventional data cleaning and checking procedures including assessment of missing data and outliers, and uni- and bivariate plausibility checks. Data verifications and if applicable corrections will be requested.

Next, a thorough description of the overall study sample and of the two randomized study arms will be conducted for the two analysis populations ITT and PP. The study population will be described statistically with regard to main captured clinical patient characteristics, e.g. age, sex, ethnicity, disease status and PCT concentration. Frequency counts will be reported for nominal variables and means with standard deviations or medians and inter-quartile ranges will be reported for numerical variables as appropriate to variable type. Baseline patient characteristics will be reported for all patients (both study arms together) as well as per-study arm.

4.3 Primary Study Hypothesis

For the primary study endpoint “**short antibiotic treatments**” (“shortABx”; proportion of patients with short antibiotic treatments of pneumonia less than 4 days) the study hypotheses for statistical inference are as follows:

H0: The probability of patients with short antibiotic treatment of pneumonia is smaller or equal in the PCT arm versus the control arm.

H1: The probability of patients with short antibiotic treatment of pneumonia is greater in the PCT arm than in the control arm.

Note that the study goal is one-sided: to validate a shortABx probability in the PCT arm that is higher than the shortABx probability in the control arm (see Section 4.4; one-sided statistical testing at 2.5% significance level controlled for multiple testing / interim analyses, see Section 2.3 and 2.5). Bayesian statistics with uninformative priors will be applied for analysis.

4.4 Primary Analysis of Antibiotic Exposure

The primary endpoint “short antibiotic treatments” will be analyzed for superiority. We will assess the differences in proportions by Bayesian analysis assuming binomially distributed events. Posterior probabilities will be computed study-arm specifically using conjugate beta-distributed and uninformative uniform priors (shape parameters $\alpha = \beta = 1$).

More specifically, the following generative model will be used:

$$\begin{aligned} N_{\text{PCT}}^s &\sim \text{Binomial}(N_{\text{PCT}}, p_{\text{PCT}}) \\ N_{\text{ctrl}}^s &\sim \text{Binomial}(N_{\text{ctrl}}, p_{\text{ctrl}}) \\ \text{priors: } p_{\text{PCT}}, p_{\text{ctrl}} &\sim \text{Uniform}(0, 1) \end{aligned}$$

with

$N_{\text{PCT}}^s, N_{\text{ctrl}}^s$: number of patients with shortABx of the PCT arm and control arm, respectively
 $N_{\text{PCT}}, N_{\text{ctrl}}$: number of patients randomized to the PCT arm and control arm, respectively
 $p_{\text{PCT}}, p_{\text{ctrl}}$: shortABx probability for patients of the PCT arm and control arm, respectively

Differences between beta-distributed study-arm specific posterior probabilities will be computed by Monte Carlo simulation with sampling from study-arm specific posterior probabilities. Success of the analysis of antibiotic exposure is specified by more than 98.5% posterior probability for more frequent short antibiotic treatments in the PCT arm than in the control arm, i.e.,

$$\text{Probability[prob(short-ABx | PCT arm)} > \text{prob(short-ABx | control arm) } > 98.5\%$$

with

$\text{prob(short-ABx | PCT arm)}$: probability of short antibiotic treatment
for patients randomized to the PCT arm,
 $\text{prob(short-ABx | control arm)}$: probability of short antibiotic treatment
for patients randomized to the control arm.

The primary analysis will be conducted based on the ITT population. The analysis will also be conducted based on the PP patient populations and ITT- and PP-results will be compared and discussed.

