	
 - Patient with prolonged or severe cardiogenic shock defined as decreased cardiac output leading to end organ injury (e.g. severe hypotension or AKI or oliguria or altered mental status or cool extremities or respiratory distress AND evidence of metabolic acidosis on lab testing), - Patient with pancreatitis, chemical pneumonitis or heat stroke - Active infection with invasive fungal pathogen (e.g. candidiasis, aspergillosis) or plasmodium falciparum malaria or mycobacteria - Patient under treatment with OKT3 antibodies, OK-432, interleukins, TNF-alpha and other drugs stimulating the release of pro-inflammatory cytokines or resulting in anaphylaxis. - Patient is under hospice care - Patient with ventilator-associated pneumonia - Patients with untreated, active, and symptomatic autoimmune disease - Patients actively enrolled in other clinical trial involving immunomodulatory therapy - Patients with empyema, abscess, or cavitary/necrotizing pneumonia
Sample Size	Bayesian adaptive design with interim analyses after enrollment of 200, 350, 550 and 650 patients and a maximum number of 700 patients (350 per study arm)
Study Sites	
 1. Massachusetts General Hospital, Department of Medicine, Boston, MA, USA 2. North Shore Medical Center, Department of Medicine, Salem, MA, USA 3. Martha's Vineyard Hospital, Department of Medicine, Oak Bluffs, MA, USA 4. Grady Memorial Hospital, Department of Medicine, Atlanta, GA, USA 5. Charlotte Hungerford Hospital, Department of Medicine, Torrington, CT, USA
Study Duration	15-24 months depending on patient recruitment per adaptive study design (see statistics section below) and 30 days follow-up.

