8.1.3 Randomization

Patients will be randomized with equal 50% probability to the two treatment arms “PCT arm” and “control arm”, see Section 6. Block randomization per study site will be applied, with random block length in order to prevent the possibility of predicting study arm assignments.

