2.2 Randomization

Patients are randomized with equal probability 1:1 to the two study arms. Randomization sequences were generated per study site and with block randomization applying varying block lengths of 2 to 4 assignments per study arm. The random sequences were generated in R with package “blockrand” version 3.5.2 and fed into the eCRF system which triggered the random assignments according to patient enrollment order.

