4.5 Secondary Analysis of CAE30

The first secondary endpoint “composite adverse events until day 30” (CAE30) will be analyzed for safety non-inferiority of the PCT arm vs. the Control arm on the basis of the PP patient population. The analysis will also be conducted on the basis of the ITT patient populations and ITT- and PP-results will be compared and discussed. Differences in proportions of CAE30 between PCT arm and Control arm will be assessed by Bayesian analysis assuming binomially distributed events. Posterior probabilities will be computed study-arm specifically using conjugate beta-distributed and

uninformative uniform priors (shape parameters $\alpha = \beta = 1$). More specifically, the following generative model will be used:

$$\begin{aligned} NE_{PCT} &\sim \text{Binomial}(N_{PCT}, p_{PCT}) \\ NE_{ctrl} &\sim \text{Binomial}(N_{ctrl}, p_{ctrl}) \\ \text{priors: } p_{PCT}, p_{ctrl} &\sim \text{Uniform}(0, 1) \end{aligned}$$

with

NE_{PCT}, NE_{ctrl} : number of patients with CAE30 of the PCT arm and Control arm, respectively

N_{PCT}, N_{ctrl} : number of patients randomized to the PCT arm and Control arm, respectively

p_{PCT}, p_{ctrl} : CAE30 probability for patients of the PCT arm and Control arm, respectively

Differences between beta-distributed study-arm specific CAE30 posterior probabilities will be computed by Monte Carlo simulation sampling CAE30 probabilities p_{PCT}, p_{ctrl} from their analytically computed study-arm specific posterior probabilities. Study success is specified by more than $\gamma = 0.985$ posterior probability for a CAE30 probability of patients of the PCT arm smaller than the CAE30 probability of the Control arm plus $M = 10\%$ (NI margin):

$$\text{Probability(CAE30 probability of PCT arm} < \text{CAE30 probability of Control arm} + M \text{)} > \gamma ,$$

or with the above introduced notation

$$\text{Probability(} p_{PCT} < p_{ctrl} + M \text{)} > \gamma .$$

See Section 2.3 for the computation of the parameter γ which was set to $\gamma = 0.985$.

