4.6 Secondary Analysis of Antibiotic Exposure

The second secondary endpoint “antibiotic exposure at discharge” will be analyzed for superiority. We will assess the differences in proportions by Bayesian analysis assuming binomially distributed events. Posterior probabilities will be computed study-arm specifically using conjugate beta-distributed and uninformative uniform priors (shape parameters $\alpha = \beta = 1$). More specifically, the same generative model will be used as the one for short antibiotic treatments (see Section 4.4). Differences between beta-distributed study-arm specific posterior probabilities will be computed by Monte Carlo simulation with sampling from study-arm specific posterior probabilities. Success of the analysis of antibiotic exposure at discharge is specified by more than $\gamma = 0.985$ posterior probability for less antibiotic exposure of the PCT arm than of the Control arm, i.e., more than $\gamma = 0.985$ probability that prescriptions of antibiotics for pneumonia are less probable for patients of the PCT arm than for patients of the Control arm:

$$\text{Probability[prob(discharge-ABx | PCT arm)} < \text{prob(discharge-ABx | Control arm)} \text{]} > \gamma$$

with

$\text{prob(discharge-ABx | PCT arm)}$: probability of prescribed antibiotics at hospital discharge for patients randomized to the PCT arm,

$\text{prob}(\text{discharge-ABx} | \text{Control arm})$: probability of prescribed antibiotics at hospital discharge for patients randomized to the Control arm,

$$\gamma = 0.985.$$

The endpoints will be tested in a hierarchical manner: first, superiority testing will be conducted for the primary endpoint shortABx (see Section 4.4). If superiority is concluded for shortABx, then non-inferiority testing will be conducted for the first secondary endpoint CAE30 (see Section 4.5). If non-inferiority is concluded for CAE30, then superiority testing will be conducted for the second secondary endpoint prescribedABx. This hierarchical testing scheme allows to test the three endpoints without correction for multiple testing.

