4.7 Sensitivity Analysis

Sensitivity analysis will be conducted to assess the robustness of primary and secondary analysis results.

- The results obtained for ITT and PP patient population will be compared and discussed.
- Differences between study-arm-specific posterior probabilities will also be determined by the following Bayesian MCMC analysis adjusting effects between study arms for covariate “site” (used for stratifying randomization). The primary study endpoint (shortABx) and the first two secondary study endpoints (CAE30, prescribedABx) will be assumed to be distributed binomially

$$\text{endpoint} \sim \text{Binomial}(1, p),$$

with probability “p” parameterized by a global intercept “a”, site-specific intercepts “ b_{site} ” and study-arm specific intercepts “ c_{arm} ”

$$\text{logit}(p) = a + b_{\text{site}} + c_{\text{arm}},$$

using uninformative priors

$$\begin{aligned} a &\sim \text{Normal}(m = 0, \sigma = 1.5), \\ b_{\text{site}} &\sim \text{Normal}(m = 0, \sigma = 0.5), \\ c_{\text{arm}} &\sim \text{Normal}(m = 0, \sigma = 0.5), \end{aligned}$$

with mean m and standard deviation σ .

Probabilities for superiority of the PCT arm vs. the control arm (shortABx, prescribedABx) will be determined from the posterior sampling distributions of model parameters c_{PCT} and c_{control} : Samples will be drawn for c_{PCT} and c_{control} from their posterior distributions, the proportion of sample pairs fulfilling the criterion $c_{\text{PCT}} > c_{\text{control}}$ (for higher probability of short antibiotic treatment in the PCT-arm vs. the control-arm) or $c_{\text{PCT}} < c_{\text{control}}$ (for lower probability of antibiotics prescribed at discharge in the PCT-arm vs. the control-arm) will be determined, and it will be assessed if the obtained proportion is above $\gamma = 0.985$ fulfilling the endpoint-specific study success criterion.

Probabilities for non-inferiority of the PCT arm vs. the control arm (CAE30) will be determined similarly but will additionally include patient bootstrap sampling from the study population and evaluation of the CAE30 success criterion on the level of probabilities for applying the non-inferiority margin $M = 10\%$: (a) draw patient site “i” from study population with replacement, (b) draw samples for model parameters b_i , c_{PCT} and c_{control} from posterior probability distributions, (c)

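### Site is a randomisation stratum but is absent from all three main analyses: conservative for the ITT superiority tests, uncertain in direction for CAE30 on the per-protocol set

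*SAP*

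**What the plan says.** SAP 2.2 describes the allocation: "Randomization sequences were generated per study site and with block randomization applying varying block lengths of 2 to 4 assignments per study arm". Protocol 8.1.3 agrees: "Block randomization per study site will be applied". The protocol synopsis lists five hospitals.

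SAP 4.4 gives the main model for shortABx: "Posterior probabilities will be computed study-arm specifically using conjugate beta-distributed and uninformative uniform priors". Each arm has one binomial count and one beta posterior. SAP 4.5 uses the same structure for CAE30, with the per-protocol (PP) population named first, and SAP 4.6 reuses the 4.4 model for prescribedABx. Protocol 8.6.2 to 8.6.4 carry the same models. None has a site term, and SAP 2.3.3, which sets gamma at 0.985, describes no site effect in its simulations.

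SAP 4.7 adds a Bayesian logistic model with site intercepts for all three endpoints, judged at the same gamma. It describes site as the covariate "used for stratifying randomization". The version history gives the reason for adding it in version 5: site was a stratification factor, and ICH and FDA guidelines call for adjustment. It remains a sensitivity analysis, alongside site-specific estimates.

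**The concern.** When allocation is balanced within site, differences between sites largely cancel out of the arm contrast. An arm-only binomial model still counts them as noise, so its posterior for the difference is wider than the design warrants. The sponsor's stated reason for adjusting applies equally to the decisive tests. Power is thin for two of the three endpoints: 75% for CAE30 and 48% for prescribedABx in SAP Table 2.6.

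CAE30 raises a separate question. Its main analysis uses the PP set. SAP 3.1 forms that set after randomisation, and several of its rules apply to the PCT arm only: timely stewardship recommendations, stopping according to the algorithm, and weekend or holiday cover. Each site has its own stewardship team (Protocol 4.1), so retention in the PCT arm could differ by site. Blocking would then no longer guarantee within-site balance in the analysed set, and pooling could mix a site difference into the safety comparison.

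**Working it through.** **Inputs from SAP 2.3.3.** Marginal rates m: shortABx 22%, CAE30 20%, prescribedABx 40%. Relative risks r: 1.9, 0.9, 0.80. PP set: a random 50%. Margin 10 points, gamma 0.985 (z = 2.170), maximum 350 per arm, success stopping at 550 and 650.

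**Arm rates.** Control = 2m/(1 + r); PCT = r × control.
- shortABx: 0.44/2.9 = 15.2%, PCT 28.8%.
- CAE30: 0.40/1.9 = 21.05%, PCT 18.95%.
- prescribedABx: 0.80/1.8 = 44.4%, PCT 35.6%.

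**The plan's own figures.** Single-look check for CAE30 at 175 per arm: SE = √[(0.2105 × 0.7895 + 0.1895 × 0.8105)/175] = 0.0427, and (0.10 + 0.02105)/0.0427 − 2.170 = 0.66, so power is 74.6%. Simulating the adaptive hierarchical design (200,000 trials) gives 98.8 / 76.0 / 48.8% against the stated 99 / 75 / 48%, and a type-I error of 2.4% against the stated value below 2.5%. The design reproduces. The simulation treats interim data as complete. A rough allowance for 25 incomplete patients gives 98.8 / 74.5 / 45.2% and 1.9%.

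**Why the ITT test is conservative.** With site shares w and site rates p, mean(1 − mean) = Σw·p(1 − p) + Var(p). The arm-only model uses the left side. Under within-site balance the true variance uses only Σw·p(1 − p).

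Assumed shares are 40/20/10/20/10%. At logit SD 0.5 the assumed site shortABx rates are 15.4, 23.9, 37.8, 31.0 and 10.7%:
- Var(p) = 0.0072 and mean(1 − mean) = 0.1715, so the variance ratio is 1 − 0.0072/0.1715 = 0.958.
- The effective critical value is 2.170/√0.958 = 2.217, a single-look error of 1.3% instead of 1.5%.

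At SD 1.0 (rates 4% to 54%) the ratio is 0.853, the critical value 2.349 and the error 0.9%.

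**Adaptive design, arm-only against site-stratified risk difference, both at 0.985:**

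| Site SD | shortABx type-I error | Power shortABx | Power CAE30 | Power prescribedABx |
|---|---|---|---|---|
| 0 | 2.4 vs 2.5% | 98.8 vs 98.8% | 76.0 vs 75.3% | 49.0 vs 49.3% |
| 0.25 | 2.4 vs 2.4% | 98.9 vs 98.9% | 75.9 vs 75.7% | 48.8 vs 50.0% |
| 0.5 | 2.1 vs 2.4% | 99.0 vs 99.1% | 76.5 vs 77.3% | 49.5 vs 52.3% |
| 0.75 | 1.9 vs 2.4% | 99.1 vs 99.3% | 76.4 vs 79.3% | 49.4 vs 55.8% |
| 1.0 | 1.5 vs 2.5% | 99.3 vs 99.6% | 76.9 vs 81.9% | 49.9 vs 60.3% |

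**CAE30 at the non-inferiority boundary** (single look, nominal 1.5%, SD 0.5). The arm-only error is 1.4% in ITT and 1.5% in a random 50% PP set, so the conservatism nearly disappears.

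Stress case, all assumed: control CAE30 rates at the five sites are 13.9, 21.7, 34.9, 28.4 and 9.5%, and the PCT arm is exactly 10 points higher at every site. Control retention is 50% everywhere. PCT retention is 70% at the two low-risk sites and 30% at the other three, 50% overall.
- The PCT site mix becomes 56/12/6/12/14%.
- Pooled PCT rate = 0.10 + 0.1722 = 27.2%; control = 20.0%. The apparent difference is 7.2 points, although the true one is 10.
- SE = √[(0.2722 × 0.7278 + 0.2002 × 0.7998)/175] = 0.0452. Error = Φ(−2.170 + 0.028/0.0452) = Φ(−1.55) = 6.0%. Simulation gives 6.2%.
- With the retention pattern reversed, the apparent difference is 12.8 points and the error 0.3%.

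A separate simulation of the 70/30 pattern gave 5.2% arm-only and 1.5% site-stratified. A milder 60/40 pattern gave 2.8% and 1.5%.

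**The case against.** A reader might infer that the omission undermines the stated error control. For the ITT superiority tests it does not: the plan promises an error below 2.5%, and ignoring site only lowers it. A positive shortABx result would stand.

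A reader might also infer that the primary endpoint gives power away. It does not: the gain from adjusting is at most 0.3 point, even at SD 1.0. The larger gains for the other two endpoints need heterogeneity that the documents neither report nor assume.

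Nor can the conservatism be extended to CAE30 on the ground that blocking removes between-site variation. That argument covers the randomised set, not a PP set selected afterwards.

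The plan also pre-specifies site-adjusted analyses of all three endpoints, and the arm-only model matches the stated marginal hypothesis. What remains is which analysis decides. That still matters, because a sensitivity analysis cannot change a test result. A site-standardised risk difference also keeps a marginal target.

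Finally, the change costs more than SAP wording: the protocol carries the same models, and the interim calculations in SAP 2.5 rest on closed-form beta-binomial predictions. This objection stands and is counted in the fix.

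**Conclusion.** The point holds in limited form. The main analyses leave out the randomisation stratum, and the sponsor's reason for adjusting is applied only in a sensitivity analysis. For shortABx and prescribedABx the effect is lost efficiency, not invalidity. The loss is negligible for shortABx and about 3 points for prescribedABx at an assumed SD of 0.5. CAE30 loses about 1 point there if its PP set is a random subset. Losses of about 10 and 5 points arise only at SD 1.0.

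For the CAE30 safety claim the direction is open. If PP retention differs by site and arm, the pooled error could fall to about 0.3% or rise to about 6% against a nominal 1.5%. The documents do not show that such a pattern occurred; the stress cases show only that the plan does not guard against it. Site adjustment would remove the between-site part and leave PP selection within a site untouched.

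All sizes rest on assumed site shares, site rates and retention patterns. This is a worthwhile improvement, not a flaw that blocks the trial.

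**What to change.** In SAP 4.4 to 4.6 and Protocol 8.6.2 to 8.6.4 (with the matching synopsis text), make a site-adjusted risk difference, standardised over the trial's site mix, the main analysis. Do this at least for CAE30 on the PP set and for prescribedABx. Keep the arm-only beta-binomial as the sensitivity analysis.

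Do not simply promote the SAP 4.7 model, for two reasons:
- Its Normal(0, 0.5) priors on the arm terms are called uninformative but imply a prior SD of 0.5 × √2 = 0.71 for the arm log odds ratio, centred on no difference.
- Its CAE30 step counts single-site draws that meet the margin, so it mixes between-site spread into the probability and does not test the difference averaged over sites.

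State the new priors explicitly. Recheck gamma = 0.985 with the adjusted analysis, with and without site heterogeneity, because its simulated type-I error (about 2.4 to 2.5%) leaves almost no slack. Use the same success criterion inside the interim predictive simulations of SAP 2.5.

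The cost is SAP and protocol wording, a rerun of the existing simulation and a less simple interim calculation. No extra patients or data are needed. Because the 350-patient interim analysis has already taken place, the change should be made and documented without reference to unblinded data.
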